Effects of Caffeinated Chewing Gum on Shot Put Performance

Document Date: Jan 05 2026

IRB approved date: August 1, 2025

Project summary

15-20 active throwers who have received professional shot put training are expected to be recruited for the study. In a randomisation crossover design, the study was divided into caffeinated chewing gum trial (CCG) and placebo trail (PL). Participants wore a heart rate monitor to record their heart rate and heart rate variability during the experiment, and were given either a caffeinated chewing gum containing 3 mg/kg of body weight (CAP trial) or a placebo chewing gum, and rested for 15 minutes. After the warm-up, the athletic ability test and shot put performance were conducted in order. Saliva samples were collected for analysis of caffeine and α -amylase before and at the end of the experiment.

Introduction

The shot put is a discipline emphasizing explosive power, requiring athletes to propel the shot to a standard height and angle within a brief timeframe to achieve optimal distance. Previous studies have shown that increased sympathetic nervous system activation can effectively enhance energy output during maximal exercise intensity and improve torque during isometric contraction of the quadriceps femoris. Research on caffeine and shot put performance remains limited. In a 2012 published in 2012, morning caffeine supplementation significantly improved alertness and throwing distance in shot put athletes. Another study found that 3 mg of caffeine per kilogram of body weight effectively enhanced several physiological indicators related to explosive power, but only marginally affected shot put distance. Considering the combined findings of these two studies, current research has not specifically examined the effects of caffeine supplementation on autonomic nervous system changes or blood and saliva biochemical indicators. Therefore, future studies that strengthen the investigation of these two areas would still hold potential for publication.

Methods

Study design

This study employed a randomized crossover, double-blind experimental design, divided into two trials: the caffeinated chewing gum trial (CCG) and a placebo trial (PL). All trials were scheduled for completion during the off-season. Off-season training featured similar schedules Monday through Friday, with weekends reserved for

rest and recovery. Consequently, trials commenced on Mondays following athletes' return from rest periods to ensure consistent pre-trial recovery states. Following the first trial, after 5 days of rest and 2 days of recovery, the second and third trials will be conducted immediately. The trial sequence will be randomized by computer.

Participants

This study plans to recruit 15-20 active throwing athletes with professional shot put training as subjects. Inclusion criteria are: 1. At least 6 years of training in shot put or related track and field throwing events. 2. No cardiovascular or joint diseases. 3. Recovered from sports injuries such as strains or sprains for at least 3 months. Exclusion criteria are: 1. Non-specialized track and field throwers. 2. Presence of cardiovascular or joint diseases, or any conditions that may be exacerbated by exercise. 3. Female and underage subjects. 4. Individuals with caffeine sensitivity. The consent form is completed after the participant has given consent. This study was conducted following the Declaration of Helsinki.

Protocol

All experiments are scheduled to commence at 3:00 PM. Upon arrival at the assembly area, participants must rest in a seated position for at least 10 minutes. Subsequently, saliva samples will be collected for subsequent biochemical analysis. Concurrently, participants will wear heart rate monitors to record heart rate and heart rate variability changes throughout the experiment. Immediately after, participants chewed caffeine gum (3 mg/kg body weight) for 10 minutes (CCG trial) or caffeine-free placebo gum (3 mg/kg body weight) for 10 minutes (PL trial) before discarding it. They then began a dynamic warm-up lasting approximately 15 minutes. For caffeine gum, chewing for 10 minutes followed by a 15-minute rest period allowed for peak salivary caffeine concentration. Following the warm-up, a second saliva sample was collected. After sample collection, participants sequentially performed maximum grip strength, vertical jump, and squat tests. After testing, subjects rested for 5 minutes before performing the shot put-specific test. Following this test, participants provided another saliva sample, concluding the entire testing protocol.

Caffeine and placebo gum

The caffeinated chewing gum employed in the present study (Military Energy Gum, Arctic Mint flavour; Stay Alert, Chicago, USA) has been utilised in previous studies(1, 2). It is estimated that a single piece of gum contains approximately 5 grams and 100 milligrams of caffeine. The placebo gum was a commercially available blue mint gum

(Lotte Gum Mint., Ltd., Tokyo, Japan). In order to administer a dose of 3 mg/kg of caffeine per unit of body weight, it was necessary to crush, grind, blend, reshape and flavor all chewing gums with 0.3 g of peppermint-flavored powder. The process was designed to ensure that the new chewing gums were comparable to the original in terms of appearance, color, flavor, weight and size. Previous studies have demonstrated that this method renders it impossible for the participant to distinguish the type of gum (1, 3).

Saliva sample collection and analysis

Saliva samples were stored in a refrigerator at -80 degrees immediately after collection. For analysis, samples were thawed and centrifuged at 4000 rpm for 5 min. 500 μ L of saliva samples were transferred to glass tubes for mass spectrometry analysis and Enzyme-linked immunosorbent assay (ELISA) analysis respectively. The analysis of saliva α -amylase concentration was conducted utilising an enzyme-linked immunosorbent assay (ELISA) with commercially available reagents (Neogen Corporation, Kentucky, USA; Salimetrics LLC, State College, PA, USA).

Statistical analysis

All data are presented as means \pm standard deviations. The Shapiro–Wilk test was utilised to evaluate the normality of the data. The grip strength and number of fall on each rounds between the two trials were analyzed using paired t-tests. The saliva caffeine and α -amylase concentration and RPE were analyzed using two-way ANOVA with repeated measures. If the interaction effect (trial \times time) were significant, the Bonferroni method was used to perform post hoc comparisons. Effect sizes were calculated using Cohen's d to quantify the magnitude of observed effects and defined as trivial (<0.20), small ($0.20\text{--}0.40$), moderate ($0.40\text{--}0.80$), and large (>0.8), respectively. The power value of each data was conducted using G*Power 3.1.9.6 software (4)

Reference

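### The planned paired t-tests and trial-by-time ANOVA carry no period term and sequence balance is not stated; if there is a period effect, the contrast is biased under an unequal split or loses power under an equal one

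*Protocol*

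**What the plan says.** Under Study design, the protocol states: "This study employed a randomized crossover, double-blind experimental design, divided into two trials". On order it says only: "The trial sequence will be randomized by computer". No blocking, ratio or counterbalancing of the CCG-first and PL-first sequences is described. Under Participants, the target is a range that includes odd numbers: "This study plans to recruit 15-20 active throwing athletes with professional shot put training as subjects".

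Under Statistical analysis, two methods are named:
- Grip strength and a count of falls per round "between the two trials were analyzed using paired t-tests".
- The saliva measures and perceived exertion come under the second method: "concentration and RPE were analyzed using two-way ANOVA with repeated measures". The only interaction named is trial by time, where time is the sampling point within a session.

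Period (first or second test day) and sequence appear in neither method.

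On spacing, Study design says: "Following the first trial, after 5 days of rest and 2 days of recovery, the second and third trials will be conducted immediately". The same section describes similar weekday training with weekends off, and Monday testing chosen to equalise recovery. The Protocol subsection sets a 3:00 PM start.

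**The concern.** Randomising the order creates two sequence groups, and each within-person CCG minus PL difference contains the period shift with a sign that depends on the group. An analysis that ignores the groups handles that shift in one of two unhelpful ways. With unequal groups, part of it is counted as treatment effect. With equal groups it cancels from the mean but stays in the spread of the differences, so the test becomes conservative and loses power. With at most 20 athletes there is little power to spare.

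The text makes a period shift possible, though it does not establish one. No familiarisation session is mentioned for the tests. The interval between sessions is described as days of rest and recovery, which sits badly with the weekday training schedule given just before it. Read literally, the week before the first session differs from the week before the second.

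**Working it through.** **Inputs.** From the protocol: two conditions, randomised order, n of 15–20, and the tests named above. It states no alpha, effect size, SD or period effect, so there is no figure of its own to reproduce. Assumed: two-sided 5%, normal differences with SD 1 within sequence, no carryover, a treatment effect of 0.75 SD, and π = 0, 0.25, 0.5 or 1.

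**Model.** Let D be CCG minus PL for one athlete and π the second-period minus first-period shift. Then D = τ + π + e if CCG is second (PC) and D = τ − π + e if CCG is first (CP).

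**Bias given the realised split.** The mean of D has expectation τ + π(nPC − nCP)/n.
- 8:8 gives 0.
- 8:7 gives (1/15)π = 0.07π in size.
- 10:5 gives (5/15)π = 0.33π.
- 11:4 gives (7/15)π = 0.47π.

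**Variance given the realised split.** The expected sample variance of D is 1 + π² × 4·nPC·nCP/[n(n − 1)]. At 8:8 the multiplier is 256/240 = 1.067. The variance is therefore 1.267 at π = 0.5 and 2.067 at π = 1, although the true sampling variance of the mean is still 1/n.

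**Power at 8:8, effect 0.75 SD (simulation).**

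| π | Paired t | Period-adjusted |
|---|---|---|
| 0 | 80% | about 80% |
| 0.25 | 78% | about 80% |
| 0.5 | 72% | about 80% |
| 1 | 49% | about 80% |

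Under the null at 8:8, the paired t-test rejects in about 3% of runs at π = 0.5 and 0.6% at π = 1. The adjusted test stays at 5%.

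**Unequal splits at n = 15 under simple randomisation, Binomial(15, 0.5).** The protocol does not say that simple randomisation is used; this is an assumption.

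| Split | Probability of this or worse | Bias at this split | Paired-t type I error, π = 0.5 to 1 |
|---|---|---|---|
| 10:5 | 30.2% | 0.33π | 6–7% |
| 11:4 | 11.8% | 0.47π | 10–17% |

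At n = 20, 13:7 or worse has probability 26.3%. Exact balance has probability 17.6% at n = 20 and is impossible at n = 15.

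**Averaged over simple randomisation, effect 0.75 SD.** The paired t-test is unbiased, with type I error of about 5% at every π tried. Power, paired against adjusted:
- n = 15: 77.1% vs 73.5% (π = 0), 74.7% vs 73.7% (π = 0.25), 67.5% vs 73.6% (π = 0.5).
- n = 20: 88.8% vs 86.8% (π = 0), 87.1% vs 87.0% (π = 0.25), 81.3% vs 86.9% (π = 0.5).

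**Cost of adjusting when π = 0.** The adjusted standard error is ½√(1/nPC + 1/nCP). At 8:8 it is 0.250, equal to 1/√16. At 10:5 it is 0.274 and at 11:4 it is 0.292, against 1/√15 = 0.258. Power goes from 80.1% to 79.7% at 8:8, from 77.1% to 71.7% at 10:5, and from 77.1% to 66.2% at 11:4.

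**The ANOVA.** These figures are for single-measure outcomes. In the trial-by-time model, a shift that is constant through a session cancels from the interaction. It does not cancel from the trial main effect or from CCG against PL at a given time point.

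**The case against.** The case for leaving the plan alone has real strength.

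- **The size of π is unknown.** At π = 0.25 the loss at 8:8 is under 2 points. Off-season timing, Monday sessions and a fixed start time all limit period differences, and athletes with at least six years of training should learn little on the throw itself, though this is less clear for grip or jump tests. This stands: the need for adjustment is conditional. These steps do not remove learning on the other tests or differences in the preceding week.
- **The bias is conditional on the split.** Under simple randomisation the paired t-test is valid on average. This also stands, but the trial will analyse one realised split, and power is still lost on average at π = 0.5.
- **Adjustment is not free.** With poor balance and no period effect, the paired t-test has more power. This stands, and is why allocation must be part of the change.
- **A randomisation list or analysis plan may supply blocking.** Possible, but the protocol itself fixes tests that would not use it.

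Some stronger readings are tempting and unsupported. A reader might attach type I error of 10–17% to a 30% chance of imbalance; those rates belong to 11:4, and 11:4 or worse has probability 11.8%. A reader might also take the harm to fall on shot put distance, but the paired t-tests are assigned to grip strength and the falls count, and no test for distance is named. Outdoor conditions cannot be used as an argument, since no venue is given. Silence on familiarisation does not show that there is none. An odd n by itself matters little: 0.07π at 8:7.

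**Conclusion.** The point holds as a conditional weakness. The named analyses ignore the period structure that the randomised order creates, and nothing in the protocol secures balanced sequences. If π is 0.25 SD or less, the practical cost is small. At π = 0.5 and 8:8 the paired t-test gives up about 8 points of power (80% to 72%), and at π = 1 about 31 points (80% to 49%). Material type I error inflation needs both a large π and a split as uneven as 11:4.

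The documents do not support saying that the treatment estimate will be biased or that the planned tests are invalid: both consequences require a period effect whose size is not given. All power figures rest on the assumed 0.75 SD effect, normal differences and no carryover. The change is worth making because it is cheap, not because the plan fails without it.

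**What to change.** 1. Allocate the CCG–PL and PL–CCG sequences 1:1 from a blocked computer list, preferably with an even number within the stated 15–20, and say so under Study design.
2. Analyse each single-measure outcome with a mixed model: treatment, period and sequence fixed, participant random. With two periods and complete data, comparing within-person period differences between the sequences is equivalent.
3. Add period to the trial-by-time model for the saliva measures and perceived exertion.
4. Reconcile the number of sessions and the description of the interval between them. A third session does not fit a two-trial design, and the rest days do not fit the weekday training schedule. The period term needs the number of periods to be clear.

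Cost: a blocked list and a few sentences of analysis text. With balanced sequences and no period effect, the loss is about 0.4 points of power. It would be about 5 points at 10:5 and 11 points at 11:4, so item 1 is part of the fix. If sequences have already been drawn, the period term can still be added; fix that choice before unblinding and report the realised split.

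### The trial-by-time repeated-measures ANOVA fixed for saliva caffeine and α-amylase drops an athlete from an analyte's analysis if any one of six values is missing; a linear mixed model would keep the rest

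*Protocol*

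**What the plan says.** **Analysis.** Statistical analysis fixes the method for the saliva outcomes: "The saliva caffeine and α -amylase concentration and RPE were analyzed using two-way ANOVA with repeated measures". The two factors are trial and time. If their interaction is significant, "the Bonferroni method was used to perform post hoc comparisons".

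**Samples.** The Protocol section under Methods describes three samples per session:
- before the gum, after seated rest: "Subsequently, saliva samples will be collected for subsequent biochemical analysis";
- after the warm-up: "Following the warm-up, a second saliva sample was collected";
- after the strength tests and the throws: "Following this test, participants provided another saliva sample, concluding the entire testing protocol".

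**Assays.** Under Saliva sample collection and analysis, "saliva samples were transferred to glass tubes for mass spectrometry analysis and Enzyme-linked immunosorbent assay (ELISA) analysis respectively". That section assigns α-amylase to ELISA, which leaves mass spectrometry for caffeine.

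**Number of sessions and samples.** Study design names two trials, caffeinated gum (CCG) and placebo (PL), but later says that "the second and third trials will be conducted immediately". The Project summary mentions saliva only before and at the end, which implies two samples per trial.

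**Size.** 15 to 20 athletes are planned. No rate of missed or insufficient samples is stated, and the protocol does not itself say that incomplete athletes are deleted.

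**The concern.** Classical two-way repeated-measures ANOVA works on a complete athlete-by-trial-by-time table. One empty cell means that the athlete's other five values for that analyte cannot be used. The third sample is reached only after the warm-up, three strength tests and the throws, and each sample has to serve two assays, so an occasional gap is plausible. A gap at the end of one session would then also remove the pre-gum and post-warm-up values of both sessions. The post-warm-up sample is the one timed close to the salivary caffeine peak that the protocol describes. With 15 to 20 athletes, each one excluded costs visible precision.

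**Working it through.** **Inputs.** Two trials (Study design); three samples per trial (Protocol section); N = 15 to 20 (Participants). The per-sample loss p is an assumption, taken from 1% to 10%. The plan has no figure of its own on this point to reproduce.

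**Step 1: cells per athlete.** 2 trials × 3 times = 6 values per analyte.

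**Step 2: does one gap remove the athlete?** Data were simulated for 15 athletes (15 × 6 = 90 values) and one value was deleted. A standard repeated-measures ANOVA routine refused to fit because the data were unbalanced. With that athlete dropped it used 84 of the 89 observed values, and the error degrees of freedom for the interaction fell from 2 × 14 = 28 to 2 × 13 = 26. A linear mixed model on the same data used all 89 values and all 15 athletes.

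**Step 3: athletes left in the ANOVA.** Two loss patterns were used: independent loss of any of the six samples, share complete = (1 − p)^6; and loss confined to the two final samples, share complete = (1 − p)^2.

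| p | (1 − p)^6 | of 15 | of 20 | (1 − p)^2 | of 15 | of 20 |
|---|---|---|---|---|---|---|
| 1% | 0.94 | 14.1 | 18.8 | 0.98 | 14.7 | 19.6 |
| 3% | 0.83 | 12.5 | 16.7 | 0.94 | 14.1 | 18.8 |
| 5% | 0.74 | 11.0 | 14.7 | 0.90 | 13.5 | 18.1 |
| 10% | 0.53 | 8.0 | 10.6 | 0.81 | 12.2 | 16.2 |

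At 1% independent loss, the chance that at least one athlete is excluded is 1 − 0.9415^15 = 60% for 15 athletes and 1 − 0.9415^20 = 70% for 20. Losing one of 15 raises a standard error by √(15/14) − 1 = 3.5%; losing three raises it by √(15/12) − 1 = 12%.

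**Step 4: precision recovered by using every sample.** The contrast is the CCG − PL difference in change from pre-gum to post-warm-up. Assumed variances are participant 1.0, participant-by-trial 0.3 and residual 0.5, treated as known. The contrast variance per complete athlete is then 4 × 0.5 = 2.0. Over 3000 simulated missingness patterns, using all available samples instead of complete athletes cut the variance by about:

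| p | any of six samples | final samples only |
|---|---|---|
| 1% | 5% | 2% |
| 3% | 13% | 6% |
| 5% | 21% | 11% |
| 10% | 39% | 20% |

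The last column can be checked by hand. If only final samples are lost, every athlete still supplies the four values in this contrast, so the reduction is close to 1 − (1 − p)^2 = 2%, 6%, 10% and 19%. Results for 15 and 20 athletes are nearly the same.

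**Step 5: if only four samples are taken,** as the Project summary implies, 0.95^4 = 0.81. At 5% loss, 12.2 of 15 or 16.3 of 20 athletes are complete. The mechanism is the same.

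**The case against.** The strongest reply is that handling of missing values usually sits in the statistical analysis plan, which is not shown, and that the protocol nowhere says it will delete incomplete athletes. That is right as far as it goes, and the lack of a missing-data rule is not the point here. The point is the method that the protocol does fix. A later plan could avoid the loss only by imputing or by departing from that method.

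Three stronger readings are tempting, and the document does not support them.
- A reader might infer that one insufficient sample costs all of an athlete's saliva data. It does not. The two analytes are separate outcomes, so a sample too small for one assay affects only that analyte's ANOVA, and the observed values can still enter the means and standard deviations.
- A reader might infer that the exclusions favour athletes who tolerated the gum and the testing. Nothing in the document shows this, and calculations that impose random loss cannot show it.
- A reader might attach the independent-loss figures to early stopping. If only final samples are at risk, the gain is about half as large.

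It is also fair that losses may be very low: these are short afternoon sessions in adult athletes with at least six years of training. Saliva is, moreover, not the throwing outcome named in the title.

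**Conclusion.** The concern holds as a minor point of analysis choice. The named ANOVA drops an athlete from an analyte's analysis for one missing value of six, and from both analyses for a wholly missed sample or an early stop. The size is unknown, because it depends entirely on a loss rate that the protocol does not give. Over an assumed 1% to 10%, the variance penalty for the contrast examined runs from about 2% (final samples only, 1%) to about 39% (any sample, 10%), and it is zero if every sample is obtained. These figures also rest on the assumed variance components and on loss unrelated to the values. The count of six follows the detailed schedule; the conflicting statements on samples and sessions would change the count but not the mechanism.

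**What to change.** In Statistical analysis, replace the repeated-measures ANOVA for saliva caffeine and α-amylase, separately for each analyte, with a linear mixed model:
- fixed effects for trial, time and trial × time;
- random participant and participant-by-trial effects;
- all available samples included;
- a small-sample degrees-of-freedom method such as Kenward–Roger.

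State that the model assumes data missing at random. For caffeine, check for unequal variance between trials, because the placebo gum contains none and equal spread is doubtful. The Bonferroni step can stay.

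The cost is a sentence or two of wording and standard software. With complete data the estimated cell means are the same as from the ANOVA and the interaction test is close to it. The match is exact only in comparable covariance settings: the ANOVA's interaction error term corresponds to also having a participant-by-time random effect, which can be added if wanted.

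No change to sampling is proposed. An additional sample at the point of stopping would alter a procedure and mix different times within one level of the time factor.

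Separately, reconcile the Project summary with the Protocol section on the number of samples per session, and the two-trial design with the mention of a third trial in Study design.

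### Salivary α-amylase: the trial-by-time ANOVA treats the pre-gum sample as an outcome level and gates the post-gum comparisons on its interaction, a valid but inefficient choice

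*Protocol*

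**What the plan says.** Under Study design the protocol is a crossover "divided into two trials: the caffeinated chewing gum trial (CCG) and a placebo trial (PL"). Under Participants: "This study plans to recruit 15-20 active throwing athletes with professional shot put training as subjects".

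The Protocol subsection of Methods gives the saliva schedule:

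- Sample 1 follows the seated rest and precedes the gum: "Subsequently, saliva samples will be collected for subsequent biochemical analysis".
- Sample 2 comes after chewing and warm-up: "Following the warm-up, a second saliva sample was collected".
- Sample 3 is taken after the shot put test and closes the session.

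The Project summary instead mentions sampling only before the experiment and at its end, which reads as two samples.

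The Statistical analysis section fixes the test, stating that saliva caffeine, α-amylase "concentration and RPE were analyzed using two-way ANOVA with repeated measures". It also fixes the gate: if the trial-by-time interaction effects "were significant, the Bonferroni method was used to perform post hoc comparisons". It describes no baseline adjustment and does not list the time levels. It gives no effect size, SD, correlation or target power.

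**The concern.** Sample 1 is a pre-treatment measurement. Read with the three-sample schedule, the ANOVA is 2 × 3, with that measurement as one level of the outcome. The interaction test has 2 degrees of freedom and compares every post-gum difference with an unadjusted, noisy baseline difference. A covariate would remove only the part of the noise that baseline predicts. The gate adds a second hurdle: a post-gum difference can be declared only if the omnibus test succeeds and then a Bonferroni comparison succeeds too.

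α-amylase matters here because the Introduction justifies the study partly by the lack of work on autonomic changes and on blood and saliva markers, and α-amylase is one of the two saliva analytes named. With 15 to 20 athletes there is little power to spare. A real effect could be reported as absent because of the choice of test.

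**Working it through.** The plan has no figure of its own to reproduce.

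**Inputs from the protocol.** Two trials; three saliva samples (one pre-gum, two post-gum); n = 15 to 20; interaction-gated Bonferroni comparisons.

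**Assumptions.** Two-sided α = 0.05. Let D(i,k) be athlete i's CCG−PL difference at sample k, with SD 1 at each sample and a common correlation ρ between samples. The true shifts are (0, 0.6, 0.6) unless stated. The Bonferroni family after the F-test is taken as the three sampling times, because the protocol does not define it. Results are from simulation, 20,000 runs where the count is recorded; separate runs agree to within about two points.

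**Step 1: the stated F-test.** With two trials, the trial-by-time interaction is the one-way repeated-measures F on D:

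F = [n Σ(D̄k − D̄)² / 2] / [Σ residual² / (2(n−1))], critical value F(0.95; 2, 2(n−1)) = 3.340 at n = 15 and 3.245 at n = 20.

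Its noncentrality is λ = n Σ(δk − δ̄)² / (1−ρ). For shifts (0, 0.6, 0.6), δ̄ = 0.4 and the sum is 0.16 + 0.04 + 0.04 = 0.24. At ρ = 0.3:

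- n = 15: λ = 15 × 0.24 / 0.7 = 5.14, power about 47%.
- n = 20: λ = 20 × 0.24 / 0.7 = 6.86, power about 61%.

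**Step 2: the full stated procedure.** Require F significant and then a Bonferroni-significant CCG−PL difference at either post-gum sample. At ρ = 0.3 this happens in about 34% (n = 15) and 51% (n = 20).

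**Step 3: baseline-adjusted comparisons.** At each post-gum sample, regress D(i,k) on D(i,1), test the intercept, and apply Bonferroni for two. The residual variance is 1 − ρ² (0.91 at ρ = 0.3), so the standardised effect is 0.6/√0.91 = 0.63. At least one post-gum sample is significant in about 66% (n = 15) and 83% (n = 20). Power at one given sample is 45% at n = 15.

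**Step 4: dependence on ρ and on the pattern of effect (n = 15).**

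| Effect | ρ | F alone | F then Bonferroni | Adjusted |
|---|---|---|---|---|
| both samples | 0.3 | 0.47 | 0.34 | 0.66 |
| both samples | 0.5 | 0.62 | 0.39 | 0.74 |
| both samples | 0.7 | 0.85 | 0.45 | 0.88 |
| both samples | 0.8 | 0.96 | not recorded | 0.96 |
| one sample | 0.3 | 0.47 | 0.28 | 0.47 |
| one sample | 0.5 | 0.62 | 0.31 | 0.55 |
| one sample | 0.7 | 0.84 | not recorded | 0.73 |

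The F column is nearly the same for both patterns because shifts (0, 0.6, 0) also give 0.04 + 0.16 + 0.04 = 0.24.

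**Step 5: a second setting.** With a shift of 0.8 SD at both post-gum samples and a single test of their baseline-adjusted mean, F against adjusted at n = 15 is 0.61 vs 0.88 (pre/post correlation 0), 0.87 vs 0.97 (0.5) and 1.00 vs 1.00 (0.8). The direction is the same, and so is the vanishing gain at high correlation.

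**Step 6: error rates.** Under sphericity the F-test rejects a true null in 0.046 to 0.052 of runs. The adjusted comparisons do so in 0.048 to 0.050 in the null settings run. Both are sound at the 5% level.

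**The case against.** The strongest reply is that this is a preference, not an error. A trial-by-time ANOVA that includes baseline asks a legitimate question: does change from the pre-gum value differ between trials? It holds its level under sphericity, and the saliva measures are not named as primary. That stands: the point is about efficiency, not validity.

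The size of the gain also rests on values the protocol does not give. The 66% is the chance of at least one significant sample out of two. Against the F-test alone, the advantage disappears at ρ = 0.8 and reverses when gum acts at one sample only at ρ = 0.5 or above. That stands too. But a significant F does not say at which sample the trials differ. The protocol needs the second step for that, and the adjusted analysis leads the full procedure in every setting tried, including the one-sample effect (0.47 vs 0.28 at ρ = 0.3). Part of that lead arises because F followed by Bonferroni spends well under 5%: the null rate of its pairwise conclusions was about 0.018 in the settings where it was recorded.

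A reader might go further and infer that no sphericity correction will be applied, so that significance is overstated. The protocol neither applies nor excludes a correction, and a SAP may name one. The same holds for a transformation and for what follows the Shapiro–Wilk test. Unequal variances alone do not break sphericity either; what matters is unequal variances of the differences between times. None of this is a finding here.

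**Conclusion.** The point holds as an efficiency weakness for α-amylase. The protocol itself fixes the test and the gate, and sets no baseline adjustment beside them. Under an effect of 0.6 SD at both post-gum samples and ρ = 0.3, the adjusted comparisons gain about 19 points over the F-test at n = 15 (66 − 47) and 22 at n = 20 (83 − 61). Over the full gated procedure they gain about 32 points at either size (66 − 34; 83 − 51). These figures depend on the assumed effect, correlation and Bonferroni family.

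The point does not extend to salivary caffeine: a true null is implausible there, and values that may lie near zero before gum and under placebo would make a log-scale model fragile.

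The number of samples is unsettled between the Project summary and the Methods. If only two are taken, the interaction has 1 degree of freedom and sphericity cannot fail, but the first sample is still pre-gum and the baseline point remains.

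**What to change.** For α-amylase, replace the gated ANOVA with this: at each post-gum sample, regress the within-athlete CCG−PL difference on the CCG−PL difference in the pre-gum sample, with period included (for example, trial order coded ±1). Report the adjusted CCG−PL difference and its confidence interval at each post-gum sample, with Bonferroni for two, whatever the omnibus interaction shows.

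If a mixed model is preferred, it needs an athlete-by-trial random term and time-specific variances. With a random athlete intercept only, the two post-gum samples of one session are wrongly treated as independent given athlete. In a null simulation at n = 15 without the baseline covariate, the familywise error after Bonferroni was 6.6%, 7.8% and 9.2% at within-trial correlations of 0.3, 0.5 and 0.8. The covariate would absorb some of that.

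Reconcile the Project summary with the three-sample schedule in Methods. If two samples is correct, one adjusted comparison remains and no Bonferroni step is needed.

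The cost is wording, with no new data. The period term takes one residual degree of freedom (13 to 12 at n = 15), which the simulations above did not include, so the adjusted power shown is slightly optimistic. The real downside is the lower power against the F-test alone if gum acts at one sample only: 0.55 vs 0.62 at ρ = 0.5, n = 15.
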